5.4. Endpoints

5.4.1. Efficacy endpoints

Migraine and headache endpoints are defined in [Table CGAX. 5.1](#). Each month is defined as a 30-day period with migraine or headache measures normalized from the visit intervals.

Table CGAX. 5.1 Migraine and Headache Endpoint Definitions

Diagnosis	Definition/Criteria
Migraine headache	
A headache, with or without aura, of \geq30 minutes duration with both of the following required features (A and B):
 
A. At least 2 of the following headache characteristics:
 
 • Unilateral location • Pulsatile quality • Moderate or severe pain intensity • Aggravation by or causing avoidance of routine physical activity

	
AND
 
B. During headache at least one of the following:
 
 • Nausea and/or vomiting • Photophobia and phonophobia 
(Definition adapted from the Standard International Headache Society [IHS] International Classification of Headache Disorders (ICHD)-3)

Probable migraine	A headache of ≥ 30 minutes duration, with or without aura, but missing one of the migraine features in the IHS ICHD-3 definition. To be exact, it meets either at least two A criteria and zero B criteria, or one A criteria and at least one B criteria.
Migraine headache day (MHD) (primary objective)	A calendar day on which a migraine or probable migraine occurred.
ICHD migraine headache day	A calendar day on which a migraine occurs.
Migraine headache attack	Beginning on any day a migraine headache or probable migraine headache is recorded and ends when a migraine-free day occurs.
Non-migraine headache	All headaches of at least 30 minutes duration not fulfilling the definition of migraine or probable migraine are classified as non-migraine headaches.
Non-migraine headache day	A calendar day on which a non-migraine headache occurred.
Headache day	A calendar day on which any type of headache occurs (including migraine, probable migraine, and non-migraine headache).
Episodic migraine	4 to 14 migraine headache days and < 15 headache days per 30-day period in the prospective baseline period.

Abbreviations: ICHD = International Classification of Headache Disorders; IHS = International Headache Society; MHD = migraine headache day.

Headache information will be collected via an ePRO diary. Patients will need to enter diary data daily beginning from Visit 2, continuing until Visit 12.

Information recorded in the ePRO diary, the possible responses and the assignment to the type of headache is presented in [Table CGAX. 5.2](#).

Table CGAX. 5.2 Electronic Patient-Reported Outcomes Diary Questions, Responses, and Assignment to Headache Type

QUESTION	RESPONSES	HEADACHE ASSIGNMENT
Q1. Yesterday, did you have a headache that lasted for thirty minutes or more?	Yes	Migraine if at least 2 migraine Criteria As and at least 1 migraine Criterion B were met.
	No ^a	
Q2. Enter the total number of hours you had a headache yesterday.	Range 1 to 24	If ≥ 1 , the headache was counted as a headache day.
Q3. Yesterday, what was the worst headache pain?	Mild	
	Moderate	Migraine Criteria A
	Severe	Migraine Criteria A
Q4. Yesterday, was the headache throbbing or pounding?	Yes	Migraine Criteria A
	No	
Q5. Yesterday, was the headache just on the right or left side of your head?	Yes	Migraine Criteria A
	No	
Q6. Yesterday, was the headache made worse by your usual daily activity (for example, walking or go upstairs)?	Yes	Migraine Criteria A
	No	
Q7. Yesterday, did you want to lay down when you had headache?	Yes	
	No	
Q8. Yesterday, did the headache affect your routine daily activities?	Yes	
	No	
Q9. Yesterday, did the headache come with sensitivity to light and sound?	Yes	Migraine Criteria B
	No	
Q10. Yesterday, did you feel sick to the stomach or throw-up with the headache?	Yes	Migraine Criteria B
	No	
Q11. Yesterday, did you take any medicine for your headache?	Yes	Medication was only counted as headache medication on a day a headache occurred. If yes, patient recorded the name, frequency, and dose of medications taken.
	No	
Q12. Yesterday, do you believe you experienced a migraine with any trigger?	Yes	
	No	
Q13. Yesterday, if you experienced a migraine with any trigger, do you think the trigger was: 
 • Weather change • Environment change • Physical discomfort • Stress • Tiredness • Speical food • Not listed above 	Weather change	
	Environment change	
	Physical discomfort	
	Stress	
	Tiredness	
	Speical food	
	Not listed above	
Q14. Yesterday, did you have your menstrual period?	Yes	
	No	

Abbreviations: Q = question.

^a If “No” was answered for Q1, then the patient skipped Q2-Q8, and only answered Q9-Q14.

Note: Patients who missed a day of data entry had the ability to make-up the missed day by reporting for the day before yesterday and then for yesterday at their next log-in.

5.4.1.1. Primary Measure: The Number of Monthly Migraine Headache Days

The primary measure is the number of monthly migraine headache days (MHD). A migraine headache day is defined as a calendar day on which a migraine or probable migraine occurs.

The primary measure of the number of monthly migraine headache days will be summarized from the daily ePRO data for each patient in that period (including 30-40 days of daily data from the baseline period prior to randomization, 3 months of daily data during the double-blind treatment phase, 3 months of daily data during the open-label treatment phase, and 4 months of daily data during the post-treatment phase).

The daily data will be aggregated, and the number of migraine headache days will be provided for each of the 30-day periods. In calculating the number of migraine headache days for each period, if the period is not equal to 30 days, the number of migraine headache days will be adjusted by multiplying the number of migraine headache days by $(30/x)$ where ‘x’ is the total number of non-missing diary days in the period.

For the 4 months of the post-treatment period (Study Period V [SP V]), the monthly interval will be derived as below. Firstly, the 2-month visit interval will be split into two one-month periods for efficacy measures. If the number of days between 2 visits (visit x+1 date - visit x date) is even, the first half will be in the first one-month period and the second half will be in the second one-month period. If the number of days between 2 visits is odd, then the days will be split similarly, but the first one-month period will have 1 day more than the second one-month period. Secondly, after the two month visit intervals are split into two one-month periods, the monthly data will be derived in the same way for each one-month period as for treatment phase. For patients who discontinued early during the post-treatment phase, if the date of discontinuation is within 30 days of previous visit date, all data between the previous visit date and the discontinuation date will go to 1 monthly period; if the date of discontinuation is more than 30 days of the previous visit date, then the first 30 days will be the first monthly period, and the rest will be considered as part of the second monthly period.

This approach to missing ePRO diary data assumes that the rate of migraine headaches per day is the same for days with missing and non-missing ePRO diary days.

The same approach will also be applied to secondary and exploratory efficacy measures that are derived from ePRO data.

Additionally, if the compliance rate for each monthly interval is $\leq 50\%$, then all endpoints to be derived from the ePRO diary data for that one-month period will be considered missing. For the post-treatment phase, the derived one-month periods (resulting from splitting two-month visit interval) will be treated similarly.

For a patient who discontinues early in the double-blind (Study Period III [SP III]) or open-label treatment phase (Study Period IV [SP IV]) or post-treatment phase (SP V), compliance rate for the last month of that study period will be calculated with a denominator of 30 days (or the actual number of days in the interval if greater than 30). For the rest of months and patients, the compliance rate will be calculated as described in Section 6.8.

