5.4.1.2. Secondary and Exploratory Efficacy Measures

The same approach to adjusting the number of days within each period to a 30-day period and the same approach to imputing monthly data based on compliance as for the primary measure will be applied to all efficacy measures that are derived from ePRO diary data and need normalization to 30-day period, including:

- **Number of ICHD migraine headache days (ICHD MHD)** is calculated as the number of calendar days in a 30-day period on which a migraine occurs. Probable migraine is excluded.
- **Number of headache days** is calculated as the number of calendar days in a 30-day period on which a headache occurs.
- **Number of moderate to severe headache days** is calculated as the number of calendar days in a 30-day period on which a headache occurs with a moderate or severe severity.
- **Number of headache hours** is calculated as the total number of headache hours in a 30-day period on which a headache occurred.
- **Number of migraine headache hours** is calculated as the total number of headache hours in a 30-day period on days when a migraine or probable migraine occurs.
- **Number of migraine headache days with acute medication use** is calculated as the number of calendar days in a 30-day period on which migraine or probable migraine occurs and acute medication is used.
- **Number of migraine attacks** per 30-day period is calculated as the number of sets of consecutive days with migraine or probable migraine separated by at least one migraine-free day. For example, a migraine or probable migraine starting on 5JAN and ending on 6JAN will result in a migraine/probable migraine-free day on 7JAN (assuming that there is no migraine/probable migraine on 7JAN). This will count as 1 migraine attack that started on 5JAN and ended on 6JAN. For a migraine attack that begins in one 30-day period but ends in another, only 1 migraine attack will be counted in the first of the 2 periods. For example, in the case of 7 days of consecutive migraine/probable migraine headache with 3 days in the baseline period and 4 days in Month 1, only 1 migraine attack will be counted in the baseline period; the 4 days of migraine/probable headache in Month 1 will not be counted as a migraine attack in Month 1.

Additional secondary and exploratory efficacy measures will be derived as follows:

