- **Mean severity of remaining migraine** will be calculated at each period (including baseline and any post-baseline periods). For the calculation of mean severity, for days

with migraine or probable migraine, severity varies from 1 to 3 with 1=mild, 2=moderate, and 3=severe. The mean severity for each period will be calculated as:

$$\frac{\text{Sum of Severity of migraine headache days in the period}}{\text{number of migraine headache days in the Period}}$$

For periods with zero migraine headache days, the mean severity is considered not applicable hence missing in the analysis data set.

- **Percent change from baseline in the number of migraine headache days** will be calculated for any post-baseline 30-day period as:

$$\frac{-1 * 100 * (\# \text{ of MHD in Month Y} - \# \text{ of MHD in baseline period})}{\# \text{ of MHD in baseline period}}$$

of MHD in Month Y and # of MHD in baseline period here are the number of migraine headache days per 30-day period in Month Y and in baseline period, respectively.

- An **X% responder** is defined as Yes, if any patient who has a $\geq X\%$ reduction in the total number of migraine headache days in a 30-day period relative to baseline period, as No if otherwise. Therefore, if the percent change from baseline in the number of migraine headache days is $\geq X\%$, the patient will be counted as an X% responder. In other words, if the response rate defined above in a month is $\geq X\%$, then the patient will be an X% responder in that month. Indicators of X% responders will be derived for X=0, 5, 10, ..., 95, and 100.
- **50% responders sustained for all 3 months during double-blind treatment phase in the number of migraine headache days** is defined as meeting 50% responder criterion in migraine headache days for Month 1 to Month 3 in the double-blind treatment phase.
- **Proportion of patients who continue to demonstrate 50% response for all 3 months during the open-label treatment period.** This analysis will include patients previously treated with galcanezumab who met 50% response criteria at Month 3 in the double-blind treatment phase (SP III) and entered the open-label treatment phase (SP IV). If a patient who discontinued early during the open-label phase (SP IV) will be counted as a non-responder.

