6.3. Handling of Dropouts or Missing Data

Two statistical approaches to handling missing data will be used as appropriate: repeated measures analyses and ANCOVA model using change from baseline to LOCF endpoint.

For the repeated measures analyses, the model parameters are simultaneously estimated using restricted likelihood estimation incorporating all of the observed data. Estimates have been shown to be unbiased when the missing data are missing at random.

Please refer to Section 5.4.1 for approach of handling missing diary data for derivation of migraine headache days and other efficacy measures (with the exception of migraine attacks) derived from ePRO data per 30-day period.

Approaches of handling missing diary data for the derivation of migraine attack

For the derivation of the number of monthly migraine attacks, the LOCF method will be used to impute the missing ePRO diary days. If the patient was migraine headache-free on the day before the missing ePRO diary day, this would be carried forward as no migraine headache day until the actual next non-missing diary day. On the other hand, if the day before the missing ePRO diary day is a migraine headache day, then it would be carried forward as migraine headache day until the next non-missing diary day. The imputation will be carried out for all the missing diary days between the first non-missing to the last day.

If the diary compliance rate for a monthly interval is $\leq 50\%$, the number of monthly migraine attacks during that month will be considered missing. Please refer to Section 6.8 for diary compliance rate calculation.

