To assess the robustness of the MMRM results to deviations from normality assumption, a sensitivity analysis for raw number of migraine headache days (total number of migraine headache days for each interval without normalization to 30-day period) will be conducted with a repeated measures negative binomial regression model fitted with SAS PROC GLIMMIX. The model will include treatment, country, month, and treatment-by-month interaction, as well as the continuous fixed covariates of baseline number of monthly migraine headache days and baseline-by-month interaction, log (number of compliant days within each month/30) as the offset in the model. In case of non-convergence, country and/or baseline-by-month interaction may be excluded from the model. Directional consistency of treatment effects from this model and the primary analysis MMRM model as specified in Section 6.10.1 will be examined.

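### SAP 5.4.1.1 triggers the 30/x diary adjustment on period length although x counts completed diary days, so read literally an exactly 30-day period with missed entries is left unscaled (minor)

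*SAP*

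**What the plan says.** SAP Section 5.4.1.1 aggregates the daily diary into monthly counts. Its scaling rule is that "if the period is not equal to 30 days, the number of migraine headache days will be adjusted by multiplying" by 30/x, and x "is the total number of non-missing diary days in the period". The same section then says that the approach "assumes that the rate of migraine headaches per day is the same for days with missing and non-missing ePRO diary days".

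Four other places bear on the rule:

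- The opening of SAP 5.4.1 says, without any condition, that a month is 30 days and that measures are normalized from the visit intervals.
- SAP 6.3 sends the reader to Section 5.4.1 "for approach of handling missing diary data for derivation of migraine headache days" and other diary measures, migraine attacks excepted.
- The negative binomial sensitivity model in SAP 6.10.2 uses "log (number of compliant days within each month/30) as the offset in the model", with no condition on period length.
- A month is set to missing only when diary compliance is 50% or less (SAP 5.4.1.1).

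On scope, SAP 5.4.1.1 adds: "The same approach will also be applied to secondary and exploratory efficacy measures that are derived from ePRO data". SAP 5.4.1.2 repeats this for a list of measures: "The same approach to adjusting the number of days within each period to a 30-day period". Responder status comes from the monthly MHD counts: if the percent reduction in a month reaches X, "then the patient will be an X% responder in that month".

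**The concern.** The condition and the multiplier refer to different quantities. Whether to scale depends on how many days lie in the period. How much to scale depends on how many of those days have a diary entry. The two agree only when every entry has been made.

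An exactly 30-day period with missed entries fails the condition. Its raw count stands, and each missed day is in effect recorded as free of migraine. No other sentence repairs this. The compliance rule only removes months at or below 50%, so a 30-day period with 16 to 29 completed days stays in the analysis.

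The sentence derives the primary endpoint and, through it, the 50% and 75% responder rates, which are key secondary endpoints. It also reaches the other diary counts normalized to 30 days. Followed literally, it gives different values for the same diary according only to the visit date. A programmer who follows the letter and one who follows the intent would produce different analysis data.

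**Working it through.** The plan gives no figure for this rule, so there is none to reproduce. The sample size does not depend on it.

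**Inputs from the documents**

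- Scaling trigger, definition of x, equal-rate assumption, removal of months at 50% compliance or less: SAP 5.4.1.1.
- Responder definition, as percent reduction from baseline: SAP 5.4.1.2.
- Dosing visits targeted 30 days apart, within 2 days either way: Protocol Section 2.
- Expected diary days counted as end date minus start date plus 1: SAP 6.8.

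The baseline of 10 MHDs and the 5 recorded MHDs are illustrative.

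**Step 1. The two readings.** Let L be the period length, x the completed diary days and m the recorded MHDs.

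- Literal: m if L = 30; m × 30/x if L is not 30.
- Consistent with the equal-rate assumption: m × 30/x for every L.

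**Step 2. One diary, two visit dates.** Baseline 10, m = 5, x = 24.

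| Period length | Literal monthly count | Reduction from baseline | 50% responder |
|---|---|---|---|
| 30 days | 5.0 | (10 - 5)/10 = 50% | Yes |
| 29 or 31 days | 5 × 30/24 = 6.25 | (10 - 6.25)/10 = 37.5% | No |

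All these months are kept: 24/30 = 80%, and even 24/32 = 75% (a 31-day gap counted with the plus 1) is above 50%.

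**Step 3. Size in an affected month.** If migraine occurs at the same rate on missed and completed days, the expected recorded count is the true count × x/30. The undercount is therefore 1 - x/30:

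- x = 27: 1 - 27/30 = 10%
- x = 24: 1 - 24/30 = 20%

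**Step 4. Effect on the responder cut-offs.** Take an affected post-baseline month with a complete or scaled baseline. The true reduction that reads as R is 1 - (1 - R)/(x/30). At x = 24:

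- R = 50%: 1 - 0.50/0.80 = 37.5%
- R = 75%: 1 - 0.25/0.80 = 68.75%

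An affected baseline works the other way, because too low a baseline makes the cut-off harder to reach. The 100% responder status of a retained month does not depend on the trigger, since 0 × 30/x = 0.

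**Step 5. Which periods are exactly 30 days?** Section 5.4.1.1 does not say how the length of a treatment-phase period is counted. If it is the difference between visit dates, the on-target 30-day gap is the unscaled case. If it is counted as in Section 6.8, visits 30 days apart give 31 days and are scaled, and visits 29 days apart become the unscaled case. Both gaps lie within the visit window, so the problem remains under either count. The documents give no distribution of visit gaps or missed entries, so the number of affected months cannot be calculated.

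**Step 6. Comparison with the rest of the SAP.** For a 30-day month with 24 entries, the equal-rate assumption implies a factor of 30/24 = 1.25. The sensitivity model enters log(24/30) as the offset, which makes the same correction. The literal primary rule applies a factor of 1. The primary analysis and its normality sensitivity analysis would then treat the same six missed days differently.

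**The case against.** The best answer is that the SAP already shows what it means. Section 5.4.1.1 defines x by diary days, presents the scaling as its handling of missing diary data and states the equal-rate assumption. The opening of 5.4.1, Section 6.3 and the offset in 6.10.2 all point the same way. At x = 30 the multiplier is 1, so a program that always divides by diary days needs no condition at all. Patients can also make up a missed day at the next log-in (note to Table CGAX.5.2), which reduces missingness. This stands, and it is why the point is minor. It does not make the sentence correct: the operative rule for the primary endpoint still gives the wrong value in a case that the visit window allows.

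A reader might go further and infer any of three things. The documents support none of them.

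- *That the plan chose to count missed days as migraine-free.* The equal-rate statement says the opposite.
- *That the primary comparison is materially biased or loses power.* The frequency of affected months is unknown, and the rule is the same in both arms. With equal compliance and equal visit spacing, proportional undercounting shrinks the mean difference toward the null. It would favor one arm only if missed entries or interval lengths differed by arm.
- *That every diary measure is affected.* Missed days for migraine attacks are filled by carrying the last observation forward (SAP 6.3), and mean severity is a ratio to MHDs that is not scaled (SAP 5.4.1.2).

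**Conclusion.** The point holds as a minor error in a stated rule. As worded, SAP 5.4.1.1 leaves an exactly 30-day period with missed entries unscaled, contrary to the SAP's own assumption and to its sensitivity model. The difference in Step 2 (5.0 against 6.25 MHDs) follows from the text alone. The undercounts of 10% and 20% and the shifted responder cut-offs also need the SAP's assumption of equal migraine rates on missed and completed days. The error can reach the primary endpoint, the 50% and 75% responder key secondaries, and the other diary counts normalized to 30 days, within the limits on scope given above. The trial-level effect is probably small and cannot be quantified from the documents.

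**What to change.** Reword the sentence in SAP 5.4.1.1 so that the trigger and the multiplier use the same quantity: multiply the recorded count by 30/x, with x the number of completed diary days, whenever x is not 30, whatever the length of the period. State that this applies to baseline and to every post-baseline month. Scaling then no longer depends on how period length is counted.

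This changes SAP wording only. It needs no new data and no new analysis, and it alters no result if the programs already divide by diary days, which should be confirmed. The SAP allows changes to itself only before unblinding. If that point has passed, the clinical study report should state which derivation was programmed.

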5.4.1.2. Secondary and Exploratory Efficacy Measures

The same approach to adjusting the number of days within each period to a 30-day period and the same approach to imputing monthly data based on compliance as for the primary measure will be applied to all efficacy measures that are derived from ePRO diary data and need normalization to 30-day period, including:

- **Number of ICHD migraine headache days (ICHD MHD)** is calculated as the number of calendar days in a 30-day period on which a migraine occurs. Probable migraine is excluded.
- **Number of headache days** is calculated as the number of calendar days in a 30-day period on which a headache occurs.
- **Number of moderate to severe headache days** is calculated as the number of calendar days in a 30-day period on which a headache occurs with a moderate or severe severity.
- **Number of headache hours** is calculated as the total number of headache hours in a 30-day period on which a headache occurred.
- **Number of migraine headache hours** is calculated as the total number of headache hours in a 30-day period on days when a migraine or probable migraine occurs.
- **Number of migraine headache days with acute medication use** is calculated as the number of calendar days in a 30-day period on which migraine or probable migraine occurs and acute medication is used.
- **Number of migraine attacks** per 30-day period is calculated as the number of sets of consecutive days with migraine or probable migraine separated by at least one migraine-free day. For example, a migraine or probable migraine starting on 5JAN and ending on 6JAN will result in a migraine/probable migraine-free day on 7JAN (assuming that there is no migraine/probable migraine on 7JAN). This will count as 1 migraine attack that started on 5JAN and ended on 6JAN. For a migraine attack that begins in one 30-day period but ends in another, only 1 migraine attack will be counted in the first of the 2 periods. For example, in the case of 7 days of consecutive migraine/probable migraine headache with 3 days in the baseline period and 4 days in Month 1, only 1 migraine attack will be counted in the baseline period; the 4 days of migraine/probable headache in Month 1 will not be counted as a migraine attack in Month 1.

Additional secondary and exploratory efficacy measures will be derived as follows:

- **Mean severity of remaining migraine** will be calculated at each period (including baseline and any post-baseline periods). For the calculation of mean severity, for days

with migraine or probable migraine, severity varies from 1 to 3 with 1=mild, 2=moderate, and 3=severe. The mean severity for each period will be calculated as:

$$\frac{\text{Sum of Severity of migraine headache days in the period}}{\text{number of migraine headache days in the Period}}$$

For periods with zero migraine headache days, the mean severity is considered not applicable hence missing in the analysis data set.

- **Percent change from baseline in the number of migraine headache days** will be calculated for any post-baseline 30-day period as:

$$\frac{-1 * 100 * (\# \text{ of MHD in Month Y} - \# \text{ of MHD in baseline period})}{\# \text{ of MHD in baseline period}}$$

of MHD in Month Y and # of MHD in baseline period here are the number of migraine headache days per 30-day period in Month Y and in baseline period, respectively.

- An **X% responder** is defined as Yes, if any patient who has a $\geq X\%$ reduction in the total number of migraine headache days in a 30-day period relative to baseline period, as No if otherwise. Therefore, if the percent change from baseline in the number of migraine headache days is $\geq X\%$, the patient will be counted as an X% responder. In other words, if the response rate defined above in a month is $\geq X\%$, then the patient will be an X% responder in that month. Indicators of X% responders will be derived for X=0, 5, 10, ..., 95, and 100.
- **50% responders sustained for all 3 months during double-blind treatment phase in the number of migraine headache days** is defined as meeting 50% responder criterion in migraine headache days for Month 1 to Month 3 in the double-blind treatment phase.
- **Proportion of patients who continue to demonstrate 50% response for all 3 months during the open-label treatment period.** This analysis will include patients previously treated with galcanezumab who met 50% response criteria at Month 3 in the double-blind treatment phase (SP III) and entered the open-label treatment phase (SP IV). If a patient who discontinued early during the open-label phase (SP IV) will be counted as a non-responder.
- **Time to first 50% response (in months)** is defined as the first month when 50% response is met. If a patient has not met 50% response during SP III, the patient will be censored at the last month of SP III where 50% response status is not missing.
- **Time to first loss of 50% response in post-treatment phase (in months)** is defined as the time from the beginning of the post-treatment phase to the first month when 50% response is no longer met during the post-treatment phase (SP V). If a patient has met 50% response during all the months of SP V, the patient will be censored at the last month where 50% response status is not missing. This analysis will be conducted only for patients who met 50% response criteria at their last injection interval and are also entered into SP V.

- **Time to initiation of treatment with a migraine preventive medication (in days) in the post-treatment phase** is defined as the disposition date of the previous study period before entering SP V to the date of start of the migraine preventive medication (based on information collected from concomitant medication electronic case report form [eCRF]) in the post-treatment phase. If a patient did not initiate preventive treatment during SP V, they will be censored at the disposition date of SP V. This analysis will be conducted only for patients who entered SP V and those who are not in concurrent preventive treatment group.
- **Number of migraine headache days with nausea and/or vomiting** is calculated as the total number of migraine headache days with an answer of “yes” to Question 10 “Yesterday, did you feel sick to the stomach or throw-up with the headache?” in a 30-day period.
- **Number of migraine headache days with photophobia and phonophobia** is calculated as the total number of migraine headache days with an answer of “yes” to Question Q9 “Yesterday, did the headache come with sensitivity to light and sound?” in a 30-day period.
- **Number of weekly migraine headache days in Month 1** is calculated as the number of migraine headache days in a 7-day period on which a migraine headache occurs. At month 1, the first 7 calendar days will be counted as week 1, the second 7 calendar days will be counted as week 2, the third 7 calendar days will be counted as week 3, and the rest of days will be counted as week 4.

